**Appendix B - Patients who Discontinue Study Medication Prior to Week 52**

Procedures	EOT 	Post - EOT 	Every 8 weeks assessment from Post-EOT WK 4 visit. Last visit at Week 52 from first dose.	
		WK 4	WK 12	→
Informed consent signature				
Eligibility Review 				
Med History/ Demographics				
Physical Exam	X	X		
Weight 				
HbsAg, anti-HCV AB, HIV				
Endogenous serum EPO Level 	X	X	X	
B12, Folate	X	X		
PK 				
ECG 	X	X		
Bone marrow aspirate and biopsy 	X			
Vital signs 	X	X	X	
ECOG Score 	X	X		
Serum Lipid Panel	X	X		
LFTs 	X	X	X	
Serum chemistry 	X	X	X	
PT, PTT	X	X		
Hepcidin	X	X	X	
Pregnancy test 	X	X		
C-reactive protein	X	X		
Recording of transfusions 	→			
CBC 	X	X	X	
Local Hemoglobin	X	X	X	
Reticulocyte count; CHr	X	X		
Iron Biomarkers 	X	X	X	
Registration/Randomization to the study				
HRQoL Questionnaires 	X	X		
Study drug dosing				
Study drug dispensation				
Dose adjustment review				
AEs/Con Meds/Procedures	→			

For footnotes please refer to [Appendix A](#)

### Appendix C – Dose Adjustment Rules During the Titration to Achieve TI – Correction Phase (Prior to Maintenance Phase)

Dose adjustment will follow as described in the table below. The down titration of the dose is allowed at any time. The maximum dose of study medication is capped at 3.5 mg/kg per dose or 400 mg, whichever is lower.

In the OL component, cohort 1 (n=8) starts at 1.5 mg/kg, (Dose Level 1) followed by cohort 2 (n=8) at 2.0 mg/kg (Dose Level 2) and finally cohort 3 (n=8) at 2.5 mg/kg (Dose Level 3). The optimal starting dose will be selected for the DB component following evaluation of the OL data. It is anticipated that for the DB component, the starting dose level will be level 2 (2.0 mg/kg) and the protocol is written to reflect this but if the OL data identifies level 1 or 3 as a more optimal starting dose, this will be implemented.

Body Weight	Dose Levels					
	approx. 1.0 mg/kg	approx. 1.5 mg/kg	approx. 2.0 mg/kg	approx. 2.5 mg/kg	approx. 3.0 mg/kg	approx. 3.5 mg/kg
45 - <70 kg	50 mg TIW	70 mg TIW	100 mg TIW	150 mg TIW	200 mg TIW*	250 mg TIW*
70-100 kg	100 mg TIW	120 mg TIW	150 mg TIW	200 mg TIW	250 mg TIW	300 mg TIW*
>100 kg	120 mg TIW	150 mg TIW	200 mg TIW	250 mg TIW	300 mg TIW	350 mg TIW **

\* Patients body weight MAY require a lower dose than listed in the table above, due to the potential for the maximum dose being exceeded. The next dose given should be at one dose level immediately below what is in the above table. In some cases, a dose escalation will NOT be allowed.

\*\* Patients with body weight  $\geq$  120 kg will receive fixed dose of 400 mg TIW at Dose Level 3.

If there is **ANY** question as to the appropriate dose to administer contact the CRA or medical monitor for guidance.

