## **3.3 Study Treatment**

### **3.3.1 Dose and Schedule**

Up to 24 patients will be enrolled in sequential dose level cohorts PRIOR to start of the DB component of the study. All patients will receive roxadustat in an OL manner. The first 8 patients will receive a starting dose of 1.5 mg/kg (Dose Level 1). The next 8 patients will receive a starting dose of 2.0 mg/kg (Dose Level 2). The last 8 patients will receive a starting dose of 2.5 mg/kg (Dose Level 3). All doses will be determined by actual patient weight on registration/randomization day.

The starting dosing table for the OL portion of the study is shown below.

Dose Level Group	Approximate Roxadustat Dose (mg/kg)	Patient Weight		
		45 to <70 kg	70 - 100 kg	> 100 kg
1	1.5	70 mg TIW	120 mg TIW	150 mg TIW
2	2.0	100 mg TIW	150 mg TIW	200 mg TIW
3	2.5	150 mg TIW	200 mg TIW	250 mg TIW

The OL is intended to optimize the starting dose for the subsequent DB component of the study in which 160 eligible lower risk MDS patients with LTB will be randomized 3:2 to roxadustat or matching placebo. It is anticipated that the starting dose level will be level 2 (2.0 mg/kg) and the protocol is written to reflect this but if the OL data identifies level 1 or 3 as a more optimal starting dose, then this will be implemented.

Patients in the DB component of the study will be randomized at an overall ratio of 3:2 roxadustat or placebo with the following stratifications:

- Serum EPO level: either  $\leq 200$  mIU/mL OR  $> 200$  mIU/mL and  $\leq 400$  mIU/mL
- IPSS-R low risk / very low risk vs. intermediate risk group classification
- RBC transfusion burden: 1pRBC/8-weeks over 16 consecutive wks vs 2-4 pRBC/8wks

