#### Dose Escalation

Following commencement of study treatment, patients are evaluated for response after 8 weeks and, if the patient has required one or more RBC transfusion in that period then the dose is increased by one dose level. After each dose adjustment, the patient remains on the dose level for a minimum of 8 weeks before further adjustment is permitted.

With the exception that the starting dose will be maintained if an erythroid response (defined as a 50% reduction in pRBC from baseline) is seen after the initial 8 weeks of dosing. A re-assessment will be done for these patients at week 12 and if transfusion independence (TI) is observed the dose will not be increased. If TI is NOT observed at this point, the dose will be increased by one dose level.

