Double-blind (DB) component: 160 eligible patients will be randomized in the double-blind component of the study. When all the randomized patients complete 28 weeks of treatment or are discontinued from study medication before this time, the analysis of the primary efficacy endpoints will be performed for a topline read-out. When all the randomized patients complete 52 weeks of treatment or are discontinued from study medication before this time, the full analysis of primary and secondary efficacy endpoints will be performed.

In this DB component, 160 eligible patients will be randomized in a 3:2 assignment ratio to roxadustat or matching placebo with the following stratification factors:

- Endogenous serum EPO level: ≤ 200 mIU/mL vs. > 200 mIU/mL and ≤ 400 mIU/mL
- IPSS-R: low risk / very low risk vs. intermediate risk classification
- RBC transfusion burden: 1 pRBC/8-weeks over 16 consecutive weeks vs. 2-4 pRBC/8-weeks

NOTE: 1-pRBC randomization will be limited to no more than 30% of the total randomized patient population

OL high-erythropoietin component: Based on the Amendment 03 of the protocol dated 30 January 2020, concurrent to DB enrollment, up to 20 patients with high serum erythropoietin levels will be enrolled in an OL exploratory cohort. Unless otherwise mentioned, patients enrolled in this high erythropoietin cohort will follow all DB study procedures including the same starting dose (2.5 mg/kg TIW), same visit schedule, etc., except that the patients will all be administered roxadustat in an OL manner. Safety and efficacy assessments (transfusion independence) will be made on an ongoing basis to facilitate decision making on whether patients with elevated serum erythropoietin levels should be allowed to participate in the DB component of the study.

The study will consist of the following visits:

Baseline Assessments: To be obtained ≤ 42 days prior to starting study drug for open-label component and double-blind component respectively.

Randomization (double-blind component only): Randomization into the double-blind component to occur on Day 1 (Week 1) prior to first dose.

Treatment: The maximum treatment duration for patients in both the open-label and double-blind components is 52 weeks.

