10.3. Dose Modification

Dose Escalation

Following commencement of study treatment, patients are evaluated for response after 8 weeks (beginning at Week 9) and, if the patient has required one or more RBC transfusion in that period then the dose is increased by one dose level based on the body weight category. After each dose adjustment, the patient remains on the dose level for a minimum of 8 weeks before further adjustment is permitted based on the next scheduled visit.

Dose Reduction

The down titration of the study treatment is allowed at any time but must be performed if any of the following criteria are met. Hb levels should be retested for confirmation every 2 weeks after a dose reduction; however, it is per investigator's discretion:

- a. Transfusion independent for ≥ 56 days consecutively and Hb ≥ 12 g/dL; or
- b. Transfusion independent for ≥ 56 days consecutively and the rate of rise of Hb ≥ 2.5 g/dL over 4 weeks.
- c. In the instance where the patient achieved TI in the initial 8-weeks of the study, or has undergone treatment with the maximum allowable dose, i.e., 400 mg TIW or 3.5mg/kg for at least 8-weeks, patient may undergo dose reduction by 1-dose level. If there were no difference in erythroid response (same transfusion burden and Hb was unchanged) at this dose level for 8-weeks compared to another lower dose level, investigator may contact Sponsor's Medical Monitor to discuss another potential dose reduction.

Dose adjustment rules for patients who have TI for ≥ 56 Days (Maintenance Phase) can be referenced to [Section 19.1](#).

The number of dose escalations will be summarized descriptively.

The number and percentage of patients who exceed maximum dose will be summarized. The maximum dose of study medication is capped at 3.5 mg/kg per dose or 400 mg, whichever is lower.

The number and percentage of patients with a prescribed dose increase and decrease will be summarized. The number and percentage of patients with an actual dose hold, increase and decrease will be summarized.

The summaries above will be presented by every cumulative 4-weeks, e.g., up to 4 weeks, up to 8 weeks, ..., up to 52 weeks and up to 52 weeks and beyond.

Dose modifications by primary investigator or by patient collected on the eCRF will be listed. Hb level meeting the dose adjustment rules will be combined in the listing.

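### Protocol Appendix C (Amendment 02): the 250 mg cell for 70-100 kg exceeds the 3.5 mg/kg cap at 70 to below 71.43 kg but lacks the warning asterisk

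*Protocol*

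**What the plan says.** Appendix C of the protocol introduces its table with "Dose adjustment will follow as described in the table below" and, in the same paragraph, sets the limit: "The maximum dose of study medication is capped at 3.5 mg/kg per dose or 400 mg, whichever is lower". The table has three weight bands (45 to below 70 kg, 70-100 kg, above 100 kg) and six dose levels, headed approximately 1.0 to 3.5 mg/kg.

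A single asterisk stands on 200 mg and 250 mg in the lightest band and on 300 mg in the 70-100 kg band. Its footnote warns that body weight may call for less than the tabulated dose because the maximum could be exceeded, and then instructs: "The next dose given should be at one dose level immediately below what is in the above table". It adds that escalation is sometimes not allowed. The 350 mg cell above 100 kg carries a separate double asterisk. The 250 mg cell in the 70-100 kg band carries no mark.

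Escalation runs through this table. After eight weeks, "if the patient has required one or more RBC transfusion in that period then the dose is increased by one dose level". SAP section 10.3 repeats the rule by weight band: "then the dose is increased by one dose level based on the body weight category". The same SAP section plans a safety count: "The number and percentage of patients who exceed maximum dose will be summarized".

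**The concern.** The asterisk tells sites where the table and the cap can conflict. A cell without one therefore reads as safe across its whole band. The 250 mg cell is not safe at the bottom of its band, and the footnote's step down from the starred 300 mg cell lands on that same cell.

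A dose given as printed to a patient in the affected range would have four consequences under the plan's own rules:

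- It meets the overdose definition among the special situations in protocol section 7.2.2.
- It should be reported within 24 hours under section 5.5.
- It falls outside the section 3.3.2 provision that otherwise excuses departures from the dosing algorithm.
- It counts in the SAP 10.3 tabulation of patients above the maximum dose.

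What is at stake is a small number of avoidable overdose reports caused by following the table. Efficacy inference is not affected.

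**Working it through.** **Inputs.** The cap is min(3.5 mg/kg × weight, 400 mg) per dose (Appendix C; the same limit is in section 5.5). Doses, bands and marks come from the Appendix C table. The 70-100 kg band includes 70 kg, because the band below it stops short of 70 kg.

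**Step 1: test every cell at the lightest weight in its band**, where mg/kg is highest (dose ÷ weight). Bold marks values above 3.5 mg/kg.

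| Band, weight tested | Level 1.0 | 1.5 | 2.0 | 2.5 | 3.0 | 3.5 |
|---|---|---|---|---|---|---|
| 45 to <70 kg, at 45 kg | 50/45 = 1.11 | 70/45 = 1.56 | 100/45 = 2.22 | 150/45 = 3.33 | 200/45 = **4.44**, starred | 250/45 = **5.56**, starred |
| 70-100 kg, at 70 kg | 100/70 = 1.43 | 120/70 = 1.71 | 150/70 = 2.14 | 200/70 = 2.86 | 250/70 = **3.57**, not starred | 300/70 = **4.29**, starred |
| >100 kg, at the excluded limit of 100 kg | 1.20 | 1.50 | 2.00 | 2.50 | 3.00 | 3.50 |

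In the heaviest band 350 mg equals the cap only at exactly 100 kg, which the band excludes, so it always stays below. The double-asterisk dose of 400 mg from 120 kg is 400/120 = 3.33 mg/kg, also within the cap. Four cells can exceed the cap, and one of the four is unmarked.

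**Step 2: size of the excess in the unmarked cell.** The dose equals the cap at 250/3.5 = 71.43 kg, so the window is 70 to below 71.43 kg, or 1.43 kg wide.

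| Weight (kg) | Cap = 3.5 × weight (mg) | Excess of 250 mg (mg) | Relative excess |
|---|---|---|---|
| 70.0 | 245.00 | 5.00 | 2.0% |
| 70.5 | 246.75 | 3.25 | 1.3% |
| 71.0 | 248.50 | 1.50 | 0.6% |
| 71.4 | 249.90 | 0.10 | 0.04% |

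**Step 3: can ordinary escalation reach it?** In the 70-100 kg row the sequence is 120, 150, 200, 250 mg from the 1.5 mg/kg level upward. The cell is therefore the third escalation from a 1.5 mg/kg start, the second from 2.0 and the first from 2.5. A 2.5 mg/kg start applies to open-label cohort 3 (protocol section 3.3.1: "The last 8 patients will receive a starting dose of 2.5 mg/kg (Dose Level 3"). SAP section 3.1 also gives it for the double-blind and high-erythropoietin components, saying that the latter "will follow all DB study procedures including the same starting dose (2.5 mg/kg TIW". Stepping every weight from 45.0 to 150.0 kg in 0.1 kg increments, one level at a time and never entering a starred cell that breaks the cap, yields one over-cap dose from any of the three starts: 250 mg at 70.0-71.4 kg.

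**Step 4: does the footnote's step-down rule work?** In the lightest band, stepping down from 250 mg reaches 200 mg, which is itself starred, so the warning repeats until 150 mg (3.33 mg/kg at 45 kg). In the 70-100 kg band, stepping down from 300 mg reaches the unmarked 250 mg cell and the warning stops one level too early.

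**The case against.** The strongest reply is that the cap is a controlling rule in the paragraph directly above the table and is repeated elsewhere in the protocol and in the SAP. The asterisk only reminds sites of it. The columns are labelled approximate, and Appendix C refers any dosing question to the CRA or medical monitor. On that reading no contradictory instruction exists, and every consequence listed requires a site to overlook a limit on the same page.

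Much of this stands. The cap does govern, and it already points to 200 mg for these patients. But the same sentence governs the three starred cells, and the sponsor still chose to flag them. An unflagged cell gives no prompt to calculate or ask. The approximate labels describe nominal dose levels and do not loosen the cap.

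Three further points limit the finding:

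- **Size.** It matters only for patients in a 1.43 kg window who still need transfusion and escalate that far. Protocol section 2.4 cites a negative QT study at up to 5 mg/kg in healthy volunteers, so no clinical harm is claimed.
- **Version.** What is shown is Amendment 02. The SAP follows Amendment 03, and the high-erythropoietin component does not appear in Amendment 02. The extension to that component, and to a 2.5 mg/kg double-blind start, holds only if the table was carried over unchanged.
- **Which weight.** The protocol fixes the weight used for the starting dose but does not say which weight applies at escalation, so exact cut-points are sharper than the dosing practice it describes.

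**Conclusion.** The concern holds as a minor drafting error in Amendment 02. The 250 mg cell for 70-100 kg is the only one of the four cap-breaking cells without the warning. The breach covers 70 to below 71.43 kg and is at most 5 mg, or 2.0%. No endpoint, estimand, power calculation or type I error rate is affected.

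The conclusion assumes that the missing asterisk is genuine and was not lost when the PDF was read. That is likely, because the mark survives on the next cell in the same row. How many patients were exposed cannot be told from the documents. It deserves correction because the table is what sites work from and the correction costs almost nothing.

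**What to change.** Add the asterisk to the 250 mg cell in the 70-100 kg row. The existing footnote then holds patients below 71.5 kg at 200 mg, which is 200/70 = 2.86 down to 200/71.4 = 2.80 mg/kg.

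Optionally, print in the footnote the minimum weights that the cap implies, rounded up to 0.1 kg:

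- 200 mg from 57.2 kg (200/3.5 = 57.14)
- 250 mg from 71.5 kg (250/3.5 = 71.43)
- 300 mg from 85.8 kg (300/3.5 = 85.71)

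The cost is one character in the table. The clinical trade-off is that patients of 70 to 71.4 kg who still need transfusion would stop at a dose about 18% to 20% below their own cap (200/245 = 0.816; 200/249.9 = 0.800). The cap already forbids them 250 mg, so the change withholds nothing the protocol allows at that level. If Amendment 03 already carries the mark, nothing further is needed.

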**Figure 3 Study Schemas**

Up to 24 patients will be enrolled in sequential dose level cohorts prior to start of the DB component of the study. All patients will receive roxadustat in an OL manner. The first 8 patients will receive a starting dose of 1.5 mg/kg (Dose Level 1). The next 8 patients will receive a starting dose of 2.0 mg/kg (Dose Level 2). The last 8 patients will receive a starting dose of 2.5 mg/kg (Dose Level 3). Each patient's starting dose will be determined by their actual weight at the registration/randomization visit. The roxadustat dose per body weight are estimates only and the exact dose will be assigned per body weight ranges as shown in the body of the protocol.

The OL component is intended to optimize the starting dose for the subsequent double-blind component of the study in which 160 eligible lower risk MDS patients with LTB will be randomized 3:2 to roxadustat or matching placebo. It is anticipated that the starting dose level

will be level 2 (2.0 mg/kg) and the protocol is written to reflect this but if the OL data suggests a lower (1.5 mg/kg) or a higher (2.5 mg/kg) dose to be a more optimal starting dose, then this will be implemented accordingly.

Patients in the DB component of the study will be randomized with the following stratifications:

- Serum EPO level: either  $\leq 200$  mIU/mL OR  $> 200$  mIU/mL and  $\leq 400$  mIU/mL
- IPSS-R low risk / very low risk vs. intermediate risk group classification
- RBC transfusion burden: 1 pRBC/8-weeks over 16 consecutive weeks vs 2-4 pRBC/8-weeks

For the OL and the DB components, dose adjustments/escalations will occur every 8 weeks at pre-defined dose level increments, with the exception that the starting dose will be maintained if an erythroid response (defined as a 50% reduction in pRBC from baseline) is seen after the initial 8 weeks of dosing. A re-assessment will be done for these patients at week 12 and if transfusion independence (TI) is observed the dose will not be increased. If TI is NOT observed at this point, the dose will be increased by one dose level. See [Appendix C](#) for details on dosing and dose adjustment.

Once transfusion independence for at least 8 continuous weeks has been achieved and the “maintenance treatment period” starts, the study drug dose should follow guidance described in [Appendix D](#).

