### 3.3.2 Dose Adjustment

There are two periods for the study drug dosing – the correction phase and the maintenance phase.

**Correction phase:** Dose adjustments/escalations will occur every 8 weeks at pre-defined dose level increments, with the exception that starting dose will be maintained if erythroid response (defined as a 50% reduction in pRBC from baseline) is seen after the initial 8 weeks of dosing. A re-assessment will be done for these patients at week 12 and if transfusion independence (TI) is observed the dose will not be increased. If TI is NOT observed at this point, the dose will be increased by one dose level (see [Appendix C](#)).

**Maintenance Phase:** Once transfusion independence for at least 8 continuous weeks ( $\geq 56$  consecutive days) has been achieved and the “maintenance treatment period” starts, the study drug dose may be escalated or reduced in pre-defined levels as described in [Appendix D](#).

During the course of the study, visits and assessments will be performed as defined in the schedule of assessments (see [Appendix A](#)).

Dose reductions can occur at any time per defined criteria (see [Appendix C](#) and [Appendix D](#)).

Dosing with study medication may be held (not given) for one single instance not to exceed 2 weeks. Please contact the medical monitor with any questions.

Given the complexities of the dose adjustment algorithm, and the need to take into consideration various clinical parameters, it is not considered a protocol deviation when study subjects are dosed based on their clinical circumstance, whether or not this is concordant with the roxadustat

dosing algorithm, unless it is related to “excessive hematopoiesis” or “Overdose” (prescribed 400 mg or > 3.5 mg/kg/dose).

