### **5.5 Overdose, Emergency Procedures and Management of Overdose**

The maximum tolerated dose of roxadustat has not been established in humans. For the purpose of this study, the maximum allowed roxadustat dose is set at 400 mg or 3.5 mg/kg/dose, whichever is lower. Any dosing of study medication in this study exceeding the maximum allowed roxadustat dose should be reported within 24 hours. The Medical Monitor should be contacted as soon as possible. Symptoms associated with overdosing, if any, will be reported as adverse events.

In the event of suspected roxadustat overdose, the patient should receive supportive care and monitoring. The Sponsor's Medical Monitor should be contacted as applicable.

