#### 7.2.2 Definition of a Serious Adverse Event

A **serious adverse event** is any AE that results in any of the following outcomes:

- Death,
- A life-threatening AEs (i.e., if in the view of the investigator or Sponsor, the patient was at immediate risk of death at the time of the event). Life-threatening does not refer to an event which hypothetically might have caused death if it were more severe,
- Inpatient hospitalization or prolongation of existing hospitalization,
- A persistent or significant incapacity or substantial disruption of the ability to conduct normal life functions,
- A congenital anomaly or birth defect, or
- Other medically important events: based upon appropriate medical judgment, important medical events that may not result in death, be life-threatening, or require hospitalization may be considered serious when, they may jeopardize the patient and may require medical or surgical intervention to prevent one of the outcomes listed in this definition. Examples of such medical events include allergic bronchospasm requiring intensive treatment in an emergency room or at home, blood dyscrasias or convulsions that do not

result in inpatient hospitalization, or the development of drug dependency or drug abuse. These events must be reported to the Sponsor similar to serious adverse events.

- Safety events of interest (“Special Situations”) on the medicinal products administered to the patient as part of the study (e.g., study drug, comparator, background therapy) that **may** require expedited reporting and/or safety evaluation include, but are not limited to:
  - Overdose of the medicinal product (exceeding the maximum allowable per dose, i.e., 400 mg or 3.5 mg/kg, whichever is lower)
  - Suspected abuse/misuse of the medicinal product
  - Inadvertent or accidental exposure to the medicinal product
  - Medication error involving the medicinal product (with or without patient/patient exposure to the Sponsor medicinal product, e.g., name confusion). However, non-clinically significant errors of this type would not require expedited reporting. The medical monitor should be contacted if any clarification is required.
  - Drug-drug interactions

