## Dose Reduction

The down titration of the study treatment is allowed at any time but must be performed if any of the following criteria are met. Hb levels should be retested for confirmation every 2 weeks after a dose reduction, however it is per investigator's discretion:

- a) Transfusion independent for  $\geq 56$  days consecutively and Hb  $\geq 12$  g/dL; or
- b) Transfusion independent for  $\geq 56$  days consecutively and the rate of rise of Hb  $\geq 2.5$  g/dL over 4 weeks.
- c) In the instance where the patient achieved TI in the initial 8-weeks of the study, or has undergone treatment with the maximum allowable dose, i.e., 400 mg TIW or 3.5 mg/kg for at least 8-weeks, patient may undergo dose reduction by 1-dose level. If there were no difference in erythroid response (same transfusion burden and Hb was unchanged) at this dose level for 8-weeks compared to another lower dose level, investigator may contact Sponsor's Medical Monitor to discuss another potential dose reduction.

This is an effort to treat patients with the lowest effective dose needed to maintain erythroid response; thus, study drug dose can be increased again if erythroid response appeared to be decreased with dose decrease.

Reduction should be to one dose level lower than the dose at which the subject is receiving.

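### Appendix C places the fixed 400 mg dose for patients of 120 kg or more at the 2.5 mg/kg level instead of the top level, and Section 3.3.2 counts the permitted 400 mg as an overdose

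*Protocol*

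**What the plan says.** **Footnote.** The last cell of the Appendix C dose table (over 100 kg, approx. 3.5 mg/kg) reads 350 mg three times weekly and carries a double asterisk. The matching footnote says that patients weighing at least "120 kg will receive fixed dose of 400 mg TIW at Dose Level 3".

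**What Dose Level 3 means.** Appendix C describes the open-label cohorts as ending with "finally cohort 3 (n=8) at 2.5 mg/kg (Dose Level 3"), and Section 3.3.1 agrees: "The last 8 patients will receive a starting dose of 2.5 mg/kg (Dose Level 3"). The starting-dose table in Section 3.3.1 and the approx. 2.5 mg/kg column of Appendix C both give 250 mg for patients over 100 kg, with no footnote marker.

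**Maximum dose and overdose.** Section 5.5 states that "the maximum allowed roxadustat dose is set at 400 mg or 3.5 mg/kg/dose, whichever is lower". Section 7.2.2 describes overdose as "exceeding the maximum allowable per dose, i.e., 400 mg or 3.5 mg/kg, whichever is lower". The dose-reduction rule in Appendix C refers to a patient who "has undergone treatment with the maximum allowable dose, i.e., 400 mg TIW or 3.5 mg/kg for at least 8-weeks". Section 3.3.2, which says when dosing outside the algorithm is not a protocol deviation, makes an exception for overdose and describes it as "prescribed 400 mg or > 3.5 mg/kg/dose".

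**The concern.** The footnote is a mandatory instruction that sets the highest dose in the trial, and it uses a defined term for a level two columns below the cell it is attached to. A site that takes the label at face value would give 400 mg where the table gives 250 mg. Dose Level 3 is not a remote case: the protocol allows it as the double-blind starting level, and SAP Section 3.1 gives 2.5 mg/kg as the double-blind starting dose. A patient of 120 kg or more could then begin at the cap with no room to escalate.

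The Section 3.3.2 problem is independent of how the footnote is read. A heavy patient correctly titrated to 400 mg under Appendix C falls within that section's description of overdose and outside its no-deviation exemption, although Sections 5.5 and 7.2.2 treat the same dose as allowed.

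**Working it through.** **Inputs.** Appendix C row for over 100 kg: 120, 150, 200, 250, 300, 350 mg for approx. 1.0, 1.5, 2.0, 2.5, 3.0, 3.5 mg/kg. Cap (Appendix C, Section 5.5): the lower of 3.5 mg/kg and 400 mg. Footnote: 400 mg from 120 kg upward.

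**Step 1: which level does 400 mg at 120 kg fit?** Dose per kg = dose ÷ weight; permitted maximum = min(3.5 × weight, 400 mg).

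| Reading of the footnote's level | mg/kg × 120 kg | Tabulated dose (per kg at 120 kg) | Fits 400 mg? |
|---|---|---|---|
| Dose Level 3 as defined, 2.5 mg/kg | 300 mg | 250 mg (2.08 mg/kg) | No; 400 ÷ 2.5 = 160 kg |
| Third column of the table, 2.0 mg/kg | 240 mg | 200 mg (1.67 mg/kg) | No; 400 ÷ 2.0 = 200 kg |
| Marked column, 3.5 mg/kg | 420 mg, capped at 400 mg | 350 mg (2.92 mg/kg) | Yes |

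400 ÷ 120 = 3.33 mg/kg, which is within the 3.5 mg/kg limit. The 400 mg cap starts to bind at 400 ÷ 3.5 = 114.3 kg, so a fixed 400 mg from 120 kg makes sense as the top-level dose.

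**Step 2: does the ladder work?** For 120 kg or more:

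- Footnote applied to Dose Level 3: 120, 150, 200, **400**, 300, 350 mg. Escalating one level from Dose Level 3 would cut the dose from 400 to 300 mg.
- Footnote applied to the marked cell: 120, 150, 200, 250, 300, **400** mg. The dose rises at every step.

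**Step 3: size of the discrepancy at 120 kg.** Against the tabulated Dose Level 3 dose, 400 ÷ 250 = 1.6. Against the marked cell, 400 ÷ 350 = 1.14, the modest increase the footnote evidently intends.

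**Step 4: whom does the 400 mg clause in Section 3.3.2 catch?** Below 114.3 kg, 400 mg already exceeds 3.5 mg/kg, so the second half of the description covers it. At 114.3 kg or more, 400 mg is exactly the permitted maximum. The 400 mg clause therefore adds only patients for whom 400 mg is allowed. The Amendment 02 summary of changes shows the same wording, so a greater-than sign lost when the file was read is unlikely.

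**Possible origin.** The Amendment 02 summary records a document-wide replacement of step by level. The third step above the anticipated 2.0 mg/kg start is 3.5 mg/kg (2.5, 3.0, 3.5). That would explain the label, but the documents do not prove it.

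**The case against.** The case for treating this as purely editorial has several parts.

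- **Sites are unlikely to be misled.** The 250 mg cell has no marker. Starting doses come from tables without the footnote, and Section 3.1 says that "the exact dose will be assigned per body weight ranges as shown in the body of the protocol". A site that follows the marker arrives at the right dose, and Appendix C tells sites to ask the CRA or medical monitor about any dosing doubt. This largely stands: the footnote hazard is one of literal reading. The advice line, however, helps only a site that notices the conflict.
- **No limit is breached.** Even the literal dose of 3.33 mg/kg at 120 kg is inside the cap. This stands.
- **Section 3.3.2 sets no dose.** It limits an exemption, and a patient dosed as Appendix C directs does not need one. Overdose reporting follows Sections 5.5 and 7.2.2, which agree. SAP Section 10.3 counts only patients who exceed the maximum, and the dosing criterion among the SAP's major deviations requires an error that led to an adverse event. This stands for the planned tables: none is shown to change. It does not remove the contradiction between sections on what an overdose is.
- **A later amendment exists.** The protocol supplied is Amendment 02. The SAP is written to Amendment 03, which is not available, and SAP Section 17 reports enrollment of 140 double-blind patients. Either text may already have been corrected, and starting-dose consequences may be past. Pairing the SAP's starting dose with the Amendment 02 footnote also mixes versions. This limits the claim about current relevance but does not make the supplied text right.

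**Conclusion.** Both points hold for the protocol as supplied. The footnote's level conflicts with its own marker, with the definition in the same appendix and with the arithmetic, and taking it literally makes the dose ladder fall on escalation. The label is therefore almost certainly the error, and the intended dose is sound. Section 3.3.2 includes the permitted maximum in its description of overdose, contrary to Sections 5.5 and 7.2.2 and to Appendix C.

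The size is small. A literal reading gives 400 mg instead of 250 mg (1.6 times) for patients of 120 kg or more, and the overdose clause wrongly captures only patients of 114.3 kg or more at the top dose. The documents do not say how many such patients there are; that they are few is an assumption. Power, type I error, the primary analysis and the SAP summary of patients exceeding the maximum are unaffected. The point should be fixed because it concerns an operative dose instruction and a safety threshold, and the correction costs almost nothing.

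**What to change.** 1. In the Appendix C footnote, replace Dose Level 3 by the approx. 3.5 mg/kg dose level, so that the ladder for 120 kg or more is 120, 150, 200, 250, 300, 400 mg three times weekly. State that Dose Level 3 remains 250 mg for every patient over 100 kg.
2. In Section 3.3.2, describe overdose as more than 400 mg or more than 3.5 mg/kg per dose, matching Sections 5.5 and 7.2.2.
3. Check that the randomization system and pharmacy dose tables follow the corrected text, and confirm whether Amendment 03 already made either change.

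The cost is two wording corrections, in an amendment or a dosing clarification letter, plus the table check. No extra data or patients are needed.
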